The study procedures involve potential risk to participants. The consent procedures will make clear all of the potential risks of study participation. The most significant risk to participants in this research is loss of privacy and unauthorized release of confidential information. This could occur if the online Zoom interviews were hacked or if data on an individual participant, or the information that he or she was participating in a study of alcohol behavior, were to be released to anyone outside the study. Some of the questions asked may be a sensitive behavior. Such questions may make the participant feel uncomfortable, or be perceived as an invasion of privacy. In addition, participants are asked to report on illegal behaviors, such as drinking or marijuana use under the legal age and driving after drinking. Answers to these questions could pose a risk if the information were known and linked to identifiable individuals. We will receive a Certificate of Confidentiality from the National Institute on Alcohol Abuse and Alcoholism to prevent disclosure of sensitive or illegal behaviors. Further, all participants will be informed of the types of questions during the initial consent/training session.

We do not ask any survey items that assess suicide, child abuse, or child neglect, so we would have no data related to these topics to report. However, if a participant discloses this information we will report it to the appropriate official/agency.

Reporting alcohol use and consequences may make participants realize they are putting themselves at risk for negative consequences, potentially causing distress. We have procedures in place for referral to resources in the community (please see below).

Alternative treatments and procedures: Alternatives to web reports of drinking and its consequences include in-person interviews or self-administered written questionnaires. We believe that our web-based and automated procedures have several advantages over alternative methods of collecting this information. Our procedures do not carry any more risk than these alternatives, and may carry less risk and burden than using self-administered paper questionnaires or having to come into our offices multiple times to complete surveys.

We have taken steps to protect participants against potential risks posed by their participation in this research. Participants will be fully informed of the range of items and the most sensitive and personal items in the consent form, and will be informed that they are free not to answer any question they wish not to answer, and can refuse to participate or withdraw from participation at any time without penalty. Participants will still be able to submit a survey with unanswered questions and will still receive full compensation when submitting a survey with unanswered questions. Psychological risks of experienced invasion of privacy or increased awareness or concern about one's behavior as a result of completing the assessments and interview and potential loss of confidentiality will be addressed as a risk in the consent documents. All data and other information in the proposed research will be maintained confidentially, but will not be anonymous due to the longitudinal nature of participation. In order to protect against risks posed by a potential loss of confidentiality, we will take the following steps: First, all data will be identified only by a unique PIN, which will be randomly generated for study purposes. PINs will be embedded in individual survey links such that PINs do not need to be entered by participants or known by participants. Identifiable information entered online (such as contact information)

will be downloaded and stored separately from participants' responses, but will be identified by the PIN. A master list of names and PINs will be stored in a password-protected database, on a password-protected computer with restricted access, and will be available only to senior research staff and the PI on this project. Electronic data (i.e. audio and video-recordings and transcripts) will be stored on password-protected secure computers only accessible to study personnel. Second, all members of the research team have received or will receive training that includes emphasis upon the importance of confidentiality of information, and all personnel on the project (including research assistants and study staff) will complete the required NIH training in protection of human research participants. All staff will sign confidentiality statements. Third, to maintain confidentiality of data submitted over the internet, participants will be required to log into a secure and HIPAA compliant servers using their unique PIN created for study purposes. The PI has extensive experience with conducting online recruitment and assessment with no adverse events ever occurring from this method of data collection or stated procedures. Fourth, we will receive a federal Certificate of Confidentiality through the Department of Health and Human Services. This certificate offers the highest protection available by law for research data. We previously used these certificates in our work with high school students, college student gamblers, drinkers, marijuana users, and those who engage in risky sexual behavior.

Participants will be informed of these risks and protections in the informed consent process. All recruitment contacts will emphasize the voluntary nature of participation, to reduce risks of experienced coercion. Fifth, to maintain confidentiality through the use of Zoom, connection to the online session will be protected using 256-bit Transport Layer Security (TLS). The use of TLS encryption will provide safety against the online training session being intruded.

Additionally, through the use of waiting rooms on Zoom, the interview facilitator will have the ability to only let into the online session the correct participant and not any unwanted guests. This will minimize the possibility of the Zoom server being hacked and the resulting loss of confidentiality. Finally, participants will be notified of the potential risk that the information provided may not be helpful, and will be provided with information about where else they might seek information about alcohol use, or receive alcohol-related services if desired.

Participants are encouraged to contact the investigators at any time to discuss any concerns they might have. Participants who express interest in seeking help for substance-related problems or for psychological distress will be offered referral information. Participants will not be restricted from seeking other alcohol or mental health education, prevention, or treatment opportunities, and we will assess for use of other services at each assessment.

A plan is in place for identifying and referring individuals who report significantly worsening alcohol use trajectories as well as consumption of potentially lethal doses of alcohol (BAC's above .35). Specifically, the baseline, 6-week post-intervention and 3, 6, and 9-month follow-up surveys will be screened for indication of significant risk based on criteria established in our prior trials of this nature and the research literature (i.e., endorsement of "I've not been able to remember large stretches of time while drinking heavily" in combination with a BAC in the past month exceeding .35%; Chung et al., 2000; 2002). Thus, both outcomes will be used to assess hazardous alcohol use for referral in combination of .35% BAC. Once identified, these individuals will be emailed local referral information. If participants meet this criterion a second

time, these individuals will be contacted by [name] within 48 hours to explain their risk and to provide referral. In our ongoing trials, we have used this procedure without incident, and have provided referrals for both alcohol and mental health treatment. Information regarding the potential for a follow-up contact by the investigators to clarify responses or provide information is included in the consent documents. Participants are also informed in the consent form that they are free to seek other services for their alcohol use. This structure is currently in place and approved at both the local and federal level on all our existing drinking and health-risk behavior studies. All participants, at the end of participation, will be provided with a brochure regarding referral resources available in the local area.

Please see Appendix C for the clinical call script.

H. Payment/Compensation - Describe any financial payments for subject participation (e.g. compensation for time and travel). Indicate any partial payment schedule for less than complete study participation. Recall that payments cannot be perceived as coercive (overpayment for time and effort). Remember: payments are NOT benefits.

Intervention. Participants can earn \$20 for baseline, \$25 for the 6-week follow-up, \$30 for the 3-month follow-up, \$35 for the 6-month follow-up, \$40 for the 9-month follow-up, meaning that participants can earn up to \$150. Upon completion of the baseline survey, participants will be mailed a Greenphire Mastercard (not yet loaded with \$20 for the online baseline survey) that can be loaded with compensation for completing future study assessments. Participants are notified in the baseline survey end page and in the frequently asked question sheet (mailed to them with their Greenphire Mastercard) that they will need to contact us via email or phone when they receive their card. At this point, we will load the money onto their Mastercard. If a participant does not call/email confirming they have received their Greenphire Mastercard within 1-2 weeks after their card was mailed, we will periodically contact them over the phone to confirm if they have received their card. In the event they have not received it after a prolonged period of time, we will re-send them another Greenphire Mastercard to their preferred mailing address. See Appendix C for what a Greenphire Mastercard looks like. For all follow-up survey payments, research team members log into the Greenphire platform, select the correct study participant, and then selects the correct amount of compensation credit to be loaded onto the card. Within 24-48 hours that amount is loaded onto the participant's Greenphire Card and available for use. Participants will receive text (up to 5) and email (up to 5) notifications when their card is loaded with payments (Appendix C) across the study. Participants will be provided Greenphire ClinCard FAQs and information on how the Greenphire ClinCard can be used (Appendix C).

Post-Intervention Interview. Participants who complete the post-intervention interview can earn \$50 and will have their payment loaded on their existing Greenphire mastercard that was used for the follow-up survey payments or will be mailed a new Greenphire Mastercard if needed. If a new card is sent, it will be used to pay them \$50 for completing the interview.

Each Greenphire Mastercard has a unique identifier. In monthly Greenphire reports, this identifier will indicate payment amount and payment date for each payment to participants. This monthly Greenphire report will verify each and every payment for compliance purposes. Greenphire has an option to request or not request social security numbers for payment. We do not request this information as it is not a requirement for Greenphire or for study purposes.

We will advise individuals without a government-issued photo ID that they will not be able to use their Greenphire Mastercard to get a cash advance at a bank.

Compensation:

Online screening: No incentive

Baseline: 45 minutes, \$20

6-week follow-up: 45 minutes, \$25

3-month follow-up: 45 minutes, \$30

6-month follow-up: 25-30 minutes, \$35 and additional incentive item*

9-month follow-up: 25-30 minutes, \$40 and additional incentive item*

Post-intervention interview: 60 minutes, \$50

*Additional incentive items: Each participant will receive an incentive item (e.g., phone pop holder, cell phone charger) valued at no more than \$10 shortly before the start of their 6-month and 9-month surveys.

Total Possible Over the Course of Intervention: \$150

Total Possible for Post-Intervention Interview: \$50

I. Subject Costs - Describe any anticipated costs to research subject. If none, state such.

Participants in the intervention condition need a smartphone for the 6 weeks of TM intervention content and the use of their phone may contribute to the use of their data use/data plan.

J. List of KEY PERSONNEL. List all individuals directly involved in the conduct, design or reporting of research involving human subjects in this study, including anyone who may be consenting subjects. This list will include the Principal Investigator, Co-Investigators, collaborating investigators, study coordinators, etc.

Name & Degree: [name].

Department: Health Behavior and Health Systems in the School of Public Health at the University of North Texas Health Science Center

Role: Principal Investigator

Responsibilities: [name] will dedicate FTE in all years and will be responsible for the overall scientific direction of the research, including design and development of protocols, assessments, materials, participant recruitment and retention, human subjects' compliance, data analysis, and dissemination of results. [name] will oversee the duties of project staff. She

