Participants who meet inclusion criteria will be emailed a study link. The link will take participants to an Informed Consent Statement and HIPAA authorization form, where they will be asked to indicate study consent through two electronic signatures: 1) study consent form, and 2) HIPAA authorization form. The electronic signatures will be requested via a text box where participants can draw their signature. If participants indicate consent to the study, they will continue to the baseline survey. The baseline survey will include questions about demographics, personality, drinking and drug use, and other health behaviors and will take approximately 45 minutes to complete. Questions in the assessments will also include topics about sexual orientation, sexual experience, sexual desire, religion, and relationship status. Participants will receive an email and text message reminder that their follow-up surveys is approaching 5 days before their scheduled invitation date. We will also mail participants a letter with an incentive item valued at no more than \$10 and call them shortly before the survey invitations are sent. If we do not receive the completed assessment at each follow-up (Baseline Assessment, 6-week, 3, 6, and 9-Month assessment), we will periodically send reminders – via email (up to 8), text (up to 8) and/or phone/voicemail (up to 3). Participants can earn \$20 for baseline, \$25 for the 6-week follow-up, \$30 for the 3-month follow-up, \$35 for the 6-month follow-up, \$40 for the 9-month follow-up.

Post-Intervention Interview.

A total of 15 randomly selected participants assigned to the intervention condition and who agreed to be contacted for future research opportunities will be compensated \$50 for the post-intervention interview.

Recruitment Stratification.

We will stratify recruitment based on age, biological sex, and ethnicity, aiming to match demographics of UNT.

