Participants in the TM Intervention condition will be provided a random selection of 2 TM per day (across 3 self-reported days they report being most likely to drink) across 6 weeks. Each TM with intervention content will be followed by a brief message with an embedded link to a one-item survey requesting the participant to rate the text from 1 ("not at all useful") to 5 ("very useful").

Assessment Only Control Condition. Participants in the assessment only control condition will not receive any TMs during the first 6 weeks of the study but will complete all of the online assessments (baseline, 6-week, 3, 6, 9-month follow-ups). Participants will know they have been assigned to this condition if they do not receive an email notification of when their TM intervention would begin and end, and if they do not receive text messages for a 6-week period.

- 1) *Data Analysis and Data Monitoring* - Describe plans for statistical analysis of data when appropriate. If a data safety monitoring committee is appropriate to protect the safety and/or welfare of subjects, describe its operation (e.g., membership, stopping rules and frequency of review).

Post-Intervention Interviews.

After the 9-Month follow-up survey, we will invite participants who were in the intervention condition and who agreed to be contacted for future research opportunities to complete an online, post-intervention interview assessing their experience of the intervention. This feedback will be used to guide future iterations of the intervention. These one-on-one interviews will be 60-minutes in duration, and participants will be compensated \$50 for their time. We will complete up to 15 post-intervention interviews. Only participants who agreed to be contacted for future research opportunities will be invited to complete this interview.

Interview Consent Document. Eligible participants will be invited by email (up to 3), phone call/voicemail (up to 3), and/or text message (up to 3) to complete the interview consent document. The interview consent document will include information about the interview purpose, procedures, and risk. The informed consent will also include information detailing the rights of study participants such as their right to not answer any questions they are uncomfortable answering and their right to withdraw (either contacting the research team through verbal [phone] or written [email] contact) from the study at any time without penalty.

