Interview Scheduling and Reminders. Participants who consent to participate in a post-intervention interview will be contacted by phone (up to 3), email (up to 3), and/or text message (up to 3) to schedule their interview time. Once the interview has been scheduled, the reminders to schedule will stop.

Once a participant has scheduled an interview, they will receive up to 2 emails and up to 2 text messages as a reminder of the date, time, and Zoom link of their scheduled interview.

Participants can decline reminders at any time if they opt to not participate in the interview.

Participants who opt out of the study will no longer receive any contacts from the research team.

Participants who do not show up for their scheduled interview will receive emails (up to 3), texts (up to 3), and phone calls (up to 3) that will provide instructions on how to reschedule for a future date/time. Participants who wish to reschedule can call and schedule on the phone with a staff member. Once a participant reschedules, the reminders to reschedule will stop. We will complete up to 15 interviews; participants who try to schedule an interview after 15 interviews have been completed will not be allowed to schedule a session.

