The interviews will follow a semi-structured interview protocol with some additional probing questions or modifications of the original questions as needed to better suit the participants' unique backgrounds and opinions. All questions will remain relevant/applicable to the study purpose and topics of interest and will not include questions that are considered more than minimal risk.

The interview questions are to be used as a general guide. Facilitators may change the order of the questions or add probing questions to gather more specific responses, but all questions will remain relevant/applicable to the study purpose and topics of interest. Since there will be variability in the type of participants in each interview, the questions may vary slightly from one interview to another. Facilitators will not include questions that are considered to be more than minimal risk style questions.

Each interview will be limited to one participant in attendance, with Drs. [name] and [name] moderating. Interviews will last 60 minutes. The interviews will have a phenomenological focus, allowing for a free-flowing discussion with flexibility for the moderator to probe participants' responses. The moderator will provide participants with a brief overview of the study and will explain that we are seeking their input before the session begins. Please note that participants will not be asked to discuss their own drinking behavior, but rather will be asked to provide feedback on the intervention they received. Questions will focus on intervention content and delivery as well as information about drinking in general on their college campus. The goal is to obtain feedback on their experience with the intervention content and delivery as additional measures of feasibility and acceptability.

Please note that participants will not be asked to discuss their own drinking behavior, but rather will be asked to provide feedback on drinking in general on their campus as well as intervention content and delivery. There is a possibility that additional topics stemming from the questions outlined in the facilitator guide will come up through the interviews. The facilitator will ensure that any other topics that are discussed fit the overall scope of the work and do not present any additional risk. Interviews will be audio and video taped and field notes will be recorded.

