After all interviews have been conducted, we will notify remaining invited participants that their participation is no longer needed.

Data Analysis and Power.

Data Analysis. In order to evaluate the pilot study, we will examine (a) recruitment and retention rates and (b) satisfaction surveys (i.e., accessible, usable, convenient, relevant, and helpful) and (c) rates of alcohol initiation and escalation, negative consequences, abstainer prototype favorability, abstainer injunctive and descriptive norms, engagement in and enjoyment of alternative activities, and endorsement of personal goals that do not involve alcohol, which will provide base rates and variance in outcomes to determine adequate power for a future clinical trial R01 application.

Feasibility will be assessed by (1) the proportion of first-year college students ages 18-19 who meet inclusion criteria and enroll for the study and (2) the proportion of participants who complete the TM intervention, the 6-week post-intervention assessment and 3, 6, and 9-month follow-ups compared to assessment only control. The length of time to recruit our target enrollment will be assessed as an outcome of feasibility.

Acceptability will be assessed with responses from a brief satisfaction survey included in the 6-week post-intervention assessment. Acceptability will be determined by (1) the proportion of participants who find the intervention acceptable (e.g., acceptability of content delivery method), usable (e.g., ease of viewing and interacting with TM intervention content), relevant (e.g., relevance of material), and helpful (e.g., finding content helpful, beneficial, important), (2) participants' ratings of individual TMs, (3) whether participants shared the texts with anyone else, (4) the proportion of participants who would recommend the study, and (5) the proportion of participants who found the program to be favorable overall. Responses from the post-intervention interviews will also be used as a measure of acceptability.

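### The protocol says the 15 interviewees are selected at random, but its invitation and booking procedure describes no draw and closes after 15 completed interviews

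*Protocol*

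**What the plan says.** The protocol's Post-Intervention Interview paragraph, next to the survey payments, describes the interviewees as "A total of 15 randomly selected participants assigned to the intervention condition", limited to those who agreed to later contact. This is the only place where random selection of interviewees is mentioned.

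The operating detail comes later:

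- **Post-Intervention Interviews:** after the 9-month survey, "we will invite participants who were in the intervention condition and who agreed to be contacted for future research opportunities". The number is a ceiling: "We will complete up to 15 post-intervention interviews".
- **Interview Consent Document:** eligible participants may be approached up to three times by each of email, phone and text.
- **Interview Scheduling and Reminders:** "participants who try to schedule an interview after 15 interviews have been completed will not be allowed to schedule a session".
- **Just before Data Analysis and Power:** once the interviews are over, "we will notify remaining invited participants that their participation is no longer needed".

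On use of the data, Data Analysis and Power states: "Responses from the post-intervention interviews will also be used as a measure of acceptability". Interview Procedure says the feedback serves "as additional measures of feasibility and acceptability". The SAP mentions neither the interviews nor how interviewees are chosen.

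**The concern.** One sentence claims a random sample. The procedure that would have to produce it contains no draw, no random order, no batch size and no rule for replacing people who do not respond. It does contain a closing rule that depends on how soon people complete the interview.

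Acceptability is one of the pilot's stated aims, and the interviews are meant to guide the next version of the intervention. Agreement to later contact is asked at screening (Future Research Opportunities), before any message is sent, so it cannot reflect experience of the programme. Response to an interview invitation after the 9-month survey can. That is the step the protocol leaves unmanaged. If the 15 were later described as randomly selected, readers would be told of a protection that the procedure does not give.

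**Working it through.** The plan gives no figure to reproduce, so the check sets the sections side by side.

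1. **Pool.** About 150 participants are randomized to the intervention (Human Subjects, Sample Size). Only those who agreed to later contact are eligible, and no agreement rate is given. If all 150 agree, 15 / 150 = 10% of the pool is interviewed. If fewer agree, the share is higher.

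2. **Invitation.** The procedure says who may be invited and through which channels. It does not say whether everyone is invited, whether invitations go out together, or in what order.

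3. **Closing rule.** Booking is refused after 15 completed interviews. For this to affect anyone, at least 15 + 1 = 16 people must have been invited. The notice to leftover invitees fits this. The plan therefore allows for more invitees than interviews.

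4. **What follows in each case:**
   - *15 or fewer respond.* The cap never binds and everyone who responds can be interviewed. Speed plays no part. The group is still self-selected, so the random label would need qualifying.
   - *More than 15 respond, with all eligible people invited together.* The interviewed group is those who consent, book and attend first.
   - *More than 15 respond, from a randomly drawn set of invitees.* The same happens within that set. A random draw of invitees does not make the first 15 completers a random sample.
   - *Random order with staged batches.* This could reconcile the claim with the cap, but no section describes it.

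5. **Count.** The Post-Intervention Interview paragraph gives 15 as the number. Specific Aims, Post-Intervention Interviews, Interview Scheduling and Reminders, and Interview Procedure treat 15 as a maximum.

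**The case against.** **The payment sentence may be the selection rule, and the later sections only logistics under it.** No section says that all eligible participants are invited at once, so first come, first served is an inference that depends on more than 15 responding. That stands. It does not remove the problem, because the draw is nowhere described and the closing rule would still act on whoever was drawn.

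**The cap may never bind, and repeated contacts bring in slower responders.** Both points stand. They limit how often the problem would occur.

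**A reader might infer that the 15 would be the participants who liked the programme most, so that acceptability is inflated.** The documents do not support this. They say nothing about who answers early, and the $50 payment, the largest single payment in the study, could prompt quick booking as easily as enthusiasm could. One can assume that 60% of invitees are favourable and book at r times the rate of the others. The favourable share of interviewees is then 0.6r / (0.6r + 0.4): 69% at r = 1.5, 75% at r = 2 and 82% at r = 3. Every input is assumed. The formula also describes unequal willingness to take part, which would affect a randomly ordered invitation list too, so it does not measure the effect of the closing rule.

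**The interviews are coded into themes and no proportion is planned from them.** This stands. They add to the 6-week satisfaction survey and the message ratings, and the SAP's acceptability analysis rests on ratings alone. Qualitative work does not require random sampling. The fault is stating a method that the procedure does not deliver.

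**Conclusion.** Wrong as written, low severity. The claim of random selection and the described procedure do not agree. If more than 15 people respond, the interviewed group is set by who completes first and is not the random sample stated. If 15 or fewer respond, what remains is ordinary self-selection.

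The size and direction of any selection are unknown, because the documents give no rates of agreement to contact, response or booking. The survey and rating measures of acceptability are untouched. A conclusion that the pilot's acceptability result is biased would go beyond the documents.

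**What to change.** **If interviews are still to be done:**

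- Put the intervention participants who agreed to later contact in one random order and keep the list.
- Invite in small batches from the top. Open the next batch only when the allowed reminders for the current one are used up.
- Log and report the numbers invited, declined and completed.
- Amend Post-Intervention Interviews and Interview Scheduling and Reminders to say this.

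This reduces selection by speed of response. It does not remove selection by refusal, which is why the counts are needed.

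**If interviews have already been done without such a draw** (the SAP is written in the past tense), remove the claim of random selection from the Post-Intervention Interview paragraph, describe a volunteer sample, and report the same counts.

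In either case, state the number of interviews consistently, as a total or as a ceiling.

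Do not block the list by how many messages each person rated. Future Research Opportunities says the contact list will not be connected to survey data, and blocking would conflict with that.

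**Cost:** a random list, staged invitations and a simple log, with no extra interviews. Scheduling may take somewhat longer; the documents give no reminder intervals from which to estimate by how much.
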